### 3.6 Interim Analyses

There will be no interim analysis on the primary endpoint. Safety analyses of secondary safety endpoints will be performed monthly and reviewed by The Data and Safety Monitoring Board (DSMB) for Phase 1 of the study. Safety endpoints and SAEs will be monitored on a continuous basis.

## 4 STATISTICAL METHODOLOGY

### 4.1 Dataset descriptions

For all subjects enrolled in the study, data sets will be generated and updated at each study visit based on information collected during routine clinical care visits. Data to be collected from routine clinical care will include:

Donor variables: Age, sex, race, ethnicity, Human Leukocyte Antigen (HLA) data, Blood type, Cause of death (if applicable), Cold ischemic time, Donor crossmatch results, Donor serologies (CMV, EBV Hepatitis B and C), DCD and ECD donor status, Cadaveric or living (related or unrelated) donor

Recipient variables: Age, sex, race, ethnicity, HLA data, Blood type, Transplant date, Recipient serologies (CMV, EBV Hepatitis B and C), Medical history including presence of diabetes mellitus, PRA, single antigen testing, and generic drug supplier.

Medications: induction immunosuppression, maintenance immunosuppression, treatment for rejection and concomitant medications.

Post-transplant follow-up: Rejection diagnosis (grade and method of confirmation) and date, Graft status and date of failure (if applicable), Cause of graft failure (if applicable), Death and Cause of death (if applicable), Dates of hospitalizations, Biopsy results and dates, Single antigen testing results and dates, as well as Episodes of infection, including type of infection, type of organism, treatment, and response to treatment..

#### **4.2 Statistical Analyses (Aim 1 only)**

The primary research hypothesis states that subjects receiving generic tacrolimus (Arm 2) would exhibit a 1-year survival rate non-inferior at a 26% margin to the rate among subjects receiving brand tacrolimus (Arm 1). The primary efficacy endpoint will be analyzed as time-to-event, with follow-up time measured in days, from the date of transplant to the date of composite endpoint. Statistical testing of time until composite event will be done for the intention-to-treat population. A Cox regression analysis (adjusting for transplant center via indicator variables) will be used to test the null hypothesis that  $H_0: HR \geq HR_0$  versus the alternative hypothesis  $H_1: HR < HR_0$  where  $HR_0$  is hazard ratio of the generic group over the brand group at the margin set at 3.54 (i.e., a 26% non-inferiority margin). The null hypothesis will be rejected if the upper bound of the 90% 2-sided confidence interval (corresponding to a 5% one-sided significance level) for HR is less than 3.54.

Secondary analyses are described next but all are considered exploratory since formal testing of hypotheses is considered dubious given the small sample sizes of stratified subjects. Additional Cox models that include indicator functions for the generic arm (with brand serving as baseline) and/or stratification based on age/race covariates will be used to estimate specific hazard ratios with 95% confidence intervals to evaluate differences among recipients in Arm 2 and risk groups. Also, individual analyses of single endpoint hazard ratios (graft rejection, failure, death) as well as point and interval estimates of group-specific survival rates at 1-year (via Kaplan-Meier and Greenwood methods) are planned without adjustment for multiple comparisons.

Standard descriptive summaries will also be used to report and compare adherence (as measured with daily medication diaries, and with the coefficient of variation of tacrolimus in subjects' blood) and immunologic endpoints (measured by the production of donor specific HLA antibodies).

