Statistical methods: The primary efficacy endpoint will be analyzed as time-to-event, with follow-up time measured in days from the date of transplant to the date of composite endpoint. Statistical testing of time until composite event will be done for the intention-to-treat population, with adjustment for center (Cox regression). Data will also be collected on subjects who are lost to follow up. The intention-to-treat population will consist of all randomized patients who received at least 1 dose of investigational drug (brand or generic tacrolimus).

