### **3.3 Criteria for Evaluation**

Primary efficacy endpoints:

The primary endpoint of this study will be the time to a composite event, which is defined as the time to first occurrence of acute rejection, or graft failure, or death. The definition of graft failure includes re-transplant, return to dialysis, and/or death. The definition of acute rejection will be based on the Banff 2007 classification. For power considerations, it is assumed that overall 13% of subjects will experience this endpoint by one year post-transplant.

Secondary efficacy endpoints:

Secondary efficacy endpoints will include individual analyses of graft rejection, failure, death, or loss-to-follow-up at 1 year after transplantation. The cause of graft failure and death will also be analyzed. In addition, these individual endpoints and the composite endpoint will be evaluated by age group (adult and elderly (>65) and ethnicity. Other endpoints will include, rejection severity, death due to organ failure, and medication adherence. Adherence will be measured with daily medication diaries, and with the coefficient of variation of tacrolimus in subjects' blood.

Secondary safety endpoints:

Secondary safety endpoints will include the need for hospitalization, infectious episodes (bacterial, fungal, and viral), development of malignancy, and development of new-onset diabetes after transplantation.

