## **5.2 Exclusion Criteria**

1. Those who receive simultaneous combined organ transplants
2. Subjects with clinically significant active infections (for example, those requiring hospitalization, or as judged by the Investigator) or malignancies
3. Recipients who are concurrently receiving belatacept or anticipate to receive belatacept as part of their immunosuppressive regimen
4. Subjects currently enrolled in another investigational device or drug study
5. WOCBP who are unwilling or unable to use an acceptable method to avoid pregnancy for the entire study period and for 6 weeks after stopping the study drug
6. Women who are breast-feeding or pregnant with a positive pregnancy test on enrollment or prior to study drug administration
7. Prisoners or subjects who are compulsorily detained (involuntarily incarcerated) for treatment of either a psychiatric or physical (e.g., infectious disease) illness must not be enrolled into this study.
8. Any psychiatric or medical condition that, in the investigator's opinion, may put the subject at significant risk, may confound the study results, or may interfere significantly with the subject's participation in the study.

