## 6.2 Study Therapy

**6.2.1 Clinical Sites:** Kidney recipients will be enrolled at UCLA, UCSD, UCI, UC Davis Medical Centers. Mechanistic studies will be performed utilizing specimens collected from all sites. Adherence will be measured with daily medication diaries, and with the coefficient of variation of tacrolimus in subjects' blood.

**6.2.2 References and comparator arms:** During phase 1 of study, following consent and randomization, the control group were prescribed brand tacrolimus and the comparator group was prescribed generic tacrolimus. The study drugs were prescribed upon discharge, but no later than 14 days after transplant. Subjects continued to receive study drug for up to one year post-transplant. During phase 2 of study, generic tacrolimus will only be prescribed as part of their regular care upon discharge but no later than 14 days after transplant.

**6.2.3 Provision of investigational drugs:** We anticipate that brand and generic tacrolimus will be provided for the entire study period for Phase 1 of the study. Generic tacrolimus will be obtained by the subject through their insurance for Phase 2 only. (See letters from Astellas - Appendix 5)

**6.2.4 Number of subjects and sample size justification:** We plan to enroll a total of 200 subjects between the four sites. Of the 200 kidney recipients at least 20 will be African American recipients. 40 randomized subjects will be on Brand and 160 subjects will be on generic.

**6.2.5 Eligible Subjects:** In Phase 1, eligible subjects will be initially randomized using a ratio of 2:1 (Brand:Generic) until 40 subjects have been enrolled into the brand medication arm (Arm 1) and 20 have been enrolled into the generic medication arm (Arm 2). In Phase 2, 140 additional eligible subjects will be enrolled without randomization onto generic tacrolimus only as part of their regular care. All subjects will be followed for 1-year post-transplant. (A split-phase randomization process is necessary due to a limited supply and narrow expiration-time window associated with the Brand medication product.)

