**6.2.6 Screening, recruiting and eligibility:** All Kidney recipients that are 1) less than 30 days pre-transplantation or 2) up to 14 days post-transplantation, but prior to discharge, who are deemed a candidate for a tacrolimus immunosuppression regimens and meet the inclusion and exclusion criteria above, are eligible for the study. They will be invited to participate and given written informed consent for enrollment. We will attempt to enroll all subjects in a 12-month time period.

**6.2.7 Study enrollment and randomization:** This randomized, prospective, open-labeled, 2-group, parallel observational study will enroll a total of 200 subjects across 4 clinical sites. During phase 1 of the study, randomization was done after the informed consent process, using a block system pre-generated by a computer and stratified by site, ethnic group, and age cohort. During phase 2 of the study, no randomization will occur, and all subjects will be placed onto standard of care generic tacrolimus.

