### 7.2 Study Visits

#### Baseline Visit

At the baseline visit, 2-14 days after transplantation, subjects will undergo screening for eligibility by review of inclusion and exclusion factors and informed consent as administered by study personnel. Subjects will be consented in the privacy of their own rooms. The PI will review the informed consent with the patients and the subjects will have ample time to ask questions. Once the subject has signed the consent form then they will be given a copy of the signed consent form. After subjects have been consented, the following steps will be taken: Randomization to Arm 1 or 2 (for Phase 1 only), review of medical history and concomitant medications, review of labs, vital sign evaluation, and physical examination. Subjects will receive a study diary to record the name of the drug, dates, and times of taking tacrolimus (see Appendix 2 for Subject Diary).

#### Visits 1,2,3,6,9, and 12

At each additional study visit (Month 1, 2, 3, 6, 9, and 12 (End of Study Visit), (see Schedule of Events below), subjects will undergo a review of medical history and concomitant medications, review of labs, vital sign evaluation and physical examination. For more details see Table 5 Study Schedule. At the 12-month visit, subjects will return the study diary, any remaining study drug, and any related study materials. The study dosing diary will be reviewed at each study visit when available.

Trough levels will be monitored throughout the study (see Table 3 for Trough Level schedule). Subjects will continue to have routine blood and urine collection to monitor kidney function as part of their standard of care treatment at UCLA, UCSD, UCI, or UC Davis. The results of a few of these labs will be collected as part of study safety labs. For more details see Appendix 1.

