### **8.2 Test products**

Phase 2 generic medication will be supplied and obtained through their insurance from their local pharmacy or hospital during transplant admission, clinic, hospitalizations, and non-scheduled study visits.

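### The primary clock starts at transplant but post-transplant enrollees are assigned on days 2–14, so pre-assignment rejections count as primary events (about 0 to +1 point of false non-inferiority if the pre-entry HR is 1 to 3.54)

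*Combined protocol and SAP*

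**What the plan says.** The Synopsis (Statistical methods) sets the primary analysis "with follow-up time measured in days from the date of transplant to the date of composite endpoint", and section 4.2 repeats this for the Cox model: "with follow-up time measured in days, from the date of transplant to the date of composite endpoint". Section 3.3 gives the endpoint as a composite, "which is defined as the time to first occurrence of acute rejection, or graft failure, or death", without limiting it to events after assignment. Section 4.1 collects rejection dates over the whole post-transplant period.

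Entry comes later for subjects enrolled after transplant. Section 7.2 states "At the baseline visit, 2-14 days after transplantation, subjects will undergo screening for eligibility", with consent and Phase 1 randomisation at that same visit. Section 6.2.7 confirms that "randomization was done after the informed consent process". Section 5.1 also admits subjects up to 30 days before transplant, but the documents give no expected share.

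No exclusion criterion names an earlier rejection. The nearest is the investigator's discretion over conditions that "may put the subject at significant risk, may confound the study results" (section 5.2).

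On when the 140 non-randomised Phase 2 subjects start the product, two places differ. Section 6.2.2 says "generic tacrolimus will only be prescribed as part of their regular care upon discharge but no later than 14 days after transplant". Section 8.2 says the generic is "obtained through their insurance from their local pharmacy or hospital during transplant admission" as well as at later contacts.

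**The concern.** Read literally, a rejection on day 5 in a subject randomised on day 10 is a primary event, although assignment cannot have caused it. The days before entry also count as time at risk, although a post-transplant enrollee had to be alive to be enrolled.

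Between randomised groups, events before assignment have an expected hazard ratio of 1. In a superiority trial that dilution is conservative. Here the null is a hazard ratio of 3.54 or more, so any pre-entry ratio below 3.54 pulls the estimate under the margin and makes a false non-inferiority claim more likely.

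Randomisation does not settle the pre-entry ratio for the whole comparison, because 140 of the 160 generic subjects are not randomised. Whether someone who has already rejected is enrolled is a matter of judgement and could differ between phases. The brand arm is small (40 × 0.13 = 5.2 expected events), so each brand event carries weight.

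**Working it through.** **Inputs.** Brand event rate 13% at one year, margin 3.54 and 5% dropout (section 3.4, Table 1). Non-inferiority is claimed if the upper 90% limit is below 3.54 (section 4.2). Allocation is 40 brand and 160 generic, of whom 140 are Phase 2 (sections 6.2.4, 6.2.5); section 3.4 instead uses 50:150. The entry window is days 2–14 (section 7.2). Pre-entry hazard ratio and entry-day distribution are not in the documents and are varied.

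**Step 1: the plan's own figures.** Yearly hazard −ln(0.87) = 0.1393. Margin 0.0411/0.0116 = 3.54. Schoenfeld power is Φ(√(D·p·(1−p))·ln 3.54 − 1.645). With D = 25 this gives 86.3% at p = 0.25 (50:150) and 81.1% at p = 0.20 (40:160). The stated power above 80% reproduces.

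**Step 2: how many early events.** 200 × (1 − exp(−0.1393·d/365)) gives 0.38 for d = 5, 0.61 for d = 8 (mean of a uniform entry day on 2–14) and 1.07 for d = 14. For the 40 brand subjects alone it is 0.12 (d = 8) and 0.21 (d = 14). These assume that all enrol after transplant.

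**Step 3: hand check of the bias.** With a post-entry ratio of 3.54 and a pre-entry ratio of 1, the time-averaged ratio is 3.54 − 2.54·d/365: 3.48 at d = 8 and 3.44 at d = 14. Expected events at the margin, multiplying by 0.975 for dropout, are 40 × 0.13 × 0.975 = 5.1 brand and 160 × (1 − 0.87^3.54) × 0.975 = 60.7 generic. The standard error of the log ratio is √(1/5.1 + 1/60.7) ≈ 0.46. The error is Φ(−1.645 + ln(3.54/3.48)/0.46) ≈ 5.4% at d = 8, and likewise about 5.7% at d = 14, against a nominal 5%. A large-sample Cox calculation gives the same (5.40% and 5.73%).

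**Step 4: simulation of the section 4.2 test.** 40:160, constant hazard, true post-entry ratio 3.54, one year from transplant, no centre adjustment, 200,000 trials. With no pre-entry difference the test already runs at 5.89%, because brand events are few; that is a separate matter.

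| Pre-entry HR | Entry | False non-inferiority | Change (points) |
|---|---|---|---|
| 1 | day 2 | 6.01% | +0.12 |
| 1 | uniform 2–14 | 6.42% | +0.53 |
| 1 | day 14 | 6.85% | +0.95 |
| 2 | uniform 2–14 | 6.20% | +0.31 |
| 2 | day 14 | 6.44% | +0.55 |
| 3.54 | either | 5.89% | 0.00 |
| 5 | uniform 2–14 | 5.64% | −0.25 |
| 5 | day 14 | 5.43% | −0.47 |

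At 50:150 with a pre-entry ratio of 1 the change is +0.58 (uniform) and +1.04 (day 14).

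**Step 5: transplant clock against delayed entry.** Separate runs of 40,000 trials (Monte Carlo standard error 0.12 point), pre-entry ratio 1 unless noted, constant hazard:

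- Uniform entry: 6.24% against 5.80%.
- All on day 14: 6.85% against 5.90%.
- Half enrolled before transplant: 6.26% against 6.02%.
- Only half of early rejectors enrolled: 6.50% against 6.21%.
- Phase 2 at ratio 3.54 from day 0 (generic from transplant), uniform entry: 5.82% against 5.79%.

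A further run of 12,000 trials gave 6.1% against 5.6% (uniform) and 6.7% against 5.9% (day 14).

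**Step 6: cost in power.** Post-entry events are 25 × (1 − 8/365) = 24.45 and 25 × (1 − 14/365) = 24.04. Schoenfeld power at 40:160 goes from 81.1% to 80.4% and 79.8%. Simulated power of the planned interval (uniform entry) goes from 72.4% to 71.7%.

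**The case against.** Transplant is the natural origin here: the 13% rate, the 26-point margin and the hypothesis are all set at one year after transplant. That stands, and is why transplant should remain the time scale. It does not supply a rule for events before entry.

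The effect is also small, about one early event or fewer at the protocol's hazard, and generally no larger than the excess the test already carries from few brand events. That stands too.

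Delayed entry does not align the clock with exposure, since Phase 1 drug is given at discharge, after randomisation. Correct, but events between entry and first dose follow assignment and belong in an intention-to-treat comparison. It also alters the endpoint for earlier rejectors, whose next event would become their primary event. This must be stated and tested in a sensitivity analysis.

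Two stronger readings are tempting. A reader might infer that any pre-entry ratio below 3.54 guarantees an inflation of at least 0.3 point. The results do not support that floor: the change is +0.12 with day-2 entry, +0.24 with half enrolled before transplant and +0.03 with Phase 2 on generic from transplant. A reader might also infer serious inflation. If 10, 20 or 30% of the one-year hazard fell in the first 14 days, the error would be 7.3, 9.1 or 11.2% (uniform entry) or 8.7, 12.3 or 16.8% (day 14), against about 6% with delayed entry. That is 2.6, 5.2 or 7.8 times the average rate. The documents neither state nor exclude it; section 3.4 uses one constant hazard. With Phase 2 on generic from transplant and uniform entry, the same assumption gives only 6.0, 6.0 and 6.3%.

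**Conclusion.** The gap is real: followed as written, the plan counts rejections that precede assignment and credits time before entry, with no rule for either. At the protocol's constant hazard, the change in false non-inferiority is about 0 to +1 percentage point for a pre-entry ratio between 1 and 3.54. At a ratio of 1 it is about +0.5 (uniform entry) and +0.9 (day 14). It is about nil if Phase 2 subjects take generic from transplant, smaller if many enrol before transplant, and reversed above 3.54. Neither direction nor size can be fixed from the documents, because the pre-entry ratio, the entry days and the Phase 2 start are open.

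The figures take the analysis set as 40:160. The Synopsis literally limits it to randomised and dosed subjects, which by section 6.2.5 would be at most 40 + 20 = 60. These must be reconciled.

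**What to change.** In section 4.2, keep transplant as the time scale and one year post-transplant as the end of follow-up, and add delayed entry. Entry is the later of transplant and randomisation (Phase 1), or the later of transplant and consent/enrolment (Phase 2). In sections 3.3 and 4.2, state that:

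- the primary analysis counts the first event after entry, and events between entry and first dose are kept as intention-to-treat events;
- subjects with an earlier rejection are at risk from entry, and pre-entry rejections are listed by arm;
- two sensitivity analyses are reported: all events from transplant, and excluding earlier rejectors;
- one-year Kaplan–Meier rates and the 13% become conditional on entry, with expected events restated (about 24.0–24.5 instead of 25 at constant hazard).

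Reconcile sections 6.2.2 and 8.2 on when Phase 2 subjects start generic, because the size of the bias and the reading of the all-events analysis depend on it. Reconcile the Synopsis analysis set with the 40:160 comparison.

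The cost is a few sentences and two sensitivity analyses. Transplant and rejection dates are already collected (section 4.1), consent forms are dated (section 10.2.1), and a randomisation date is needed only for Phase 1. The downsides are slightly fewer events (Schoenfeld power about 81% to 80%) and, if Phase 2 subjects already take generic, their rejections before consent would move to the sensitivity analysis.

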## **3 STUDY DESIGN AND EVALUATION**

### **3.1 Study Design**

A prospective, randomized, open-label, multicenter, parallel, observational study to compare the safety and efficacy of brand versus generic tacrolimus in 200 kidney transplant recipients over a one-year follow up period. All subjects will receive other immunosuppressive medications including induction therapy (thymoglobulin, basiliximab, or no induction) and maintenance, including mycophenolate mofetil and corticosteroid therapy as directed by standard-of-care at each center. Their medication information will be recorded in their study files.

The Phase 1 portion of this study consist of 2 Arms:

Arm 1: Brand Tacrolimus (Prograf) for entire study duration (12 months)

Arm 2: Generic Tacrolimus for entire study duration (12 months)

Additionally, the study consists of 2 Phases:

Phase 1: Subjects have been randomized into either Arm 1 or Arm 2 medication. Once 40 subjects have been enrolled onto Phase 1, Phase 2 will commence.

Phase 2: Subjects will no longer be randomized. All subjects will be enrolled onto generic tacrolimus because they have elected to receive generic tacrolimus (standard of care from the subject's insurance).

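### The primary Cox model adjusts for centre but omits ethnic group and age cohort, so any age or ethnic difference between the brand arm and the non-randomised Phase 2 subjects enters the primary hazard ratio

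*Combined protocol and SAP*

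**What the plan says.** Section 6.2.7 says that Phase 1 randomisation used blocks "stratified by site, ethnic group, and age cohort". Section 4.2 carries only the first of these factors into the confirmatory model: "A Cox regression analysis (adjusting for transplant center via indicator variables) will be used to test the null hypothesis". The Synopsis agrees, testing "with adjustment for center (Cox regression"). Age and race come later in section 4.2, in additional models where "stratification based on age/race covariates will be used to estimate specific hazard ratios". That paragraph calls all secondary analyses exploratory because the stratified samples are small.

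The arms are built in two steps. Under section 6.2.5, "eligible subjects will be initially randomized using a ratio of 2:1 (Brand:Generic) until 40 subjects have been enrolled into the brand medication arm" and 20 into the generic arm. Then "140 additional eligible subjects will be enrolled without randomization onto generic tacrolimus only as part of their regular care". Section 3.1 gives the reason for Phase 2 treatment: "All subjects will be enrolled onto generic tacrolimus because they have elected to receive generic tacrolimus", as their insurance's standard of care. The primary comparison in section 4.2 is Arm 2 against Arm 1, with no phase term and no restriction to randomised subjects. The Synopsis, however, defines the intention-to-treat population as randomised patients who took at least one dose.

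**The concern.** A primary model normally carries the factors used to stratify randomisation. This one carries one of three and gives no reason for dropping the others. In a fully randomised trial the consequence would be small. Here 140/160 = 87.5% of the generic arm is enrolled without randomisation, so the stratified blocks balance age and ethnicity only among the 60 Phase 1 subjects.

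If either factor predicts rejection, graft failure or death, and its mix differs between the brand and Phase 2 subjects, the difference becomes part of the primary HR. More high-risk subjects in the brand arm would make generic look better than it is, which is the dangerous direction in a non-inferiority test. The exploratory age/race models cannot correct this, because the decision rests only on whether the primary model's upper 90% limit is below 3.54.

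**Working it through.** **Inputs from the documents.** Arms 40/160 (6.2.4, 6.2.8), of which 40 + 20 are randomised and 140 are not (6.2.5). Brand event rate 13% at one year, yearly hazard 0.14 (3.4). Dropout 5% (Table 1). Margin HR 3.54, one-sided 5% (4.2). Four centres, so three indicators.

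**Assumed inputs.** The documents give no age or ethnic mix by phase and no HR for either factor. All such values below are assumptions and show direction and rough size only.

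**1. The plan's own power.** Power = Φ(√(d·p·(1−p))·ln 3.54 − 1.645), where d is events and p the brand share.
- Section 3.4 (50/150, 25 events): √(25 × 0.25 × 0.75) = 2.165; 2.165 × 1.264 − 1.645 = 1.092; power 86.3%. The stated >80% is reproduced.
- 40/160, 25 events: √(25 × 0.20 × 0.80) = 2.000; power 81.2%.

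**2. Omission under pure randomisation.** Simulation with 200 subjects randomised 40/160 and an assumed HR of 2 for each factor (15% elderly, 10% in a higher-risk ethnic group):
- True HR 1: large-sample HR 1.00 with centre only and 1.00 with both factors added.
- True HR 3.54: 3.42 against 3.50. The gap between the two models is the attenuation.
- Non-inferiority declared at the margin: 6.5% against 5.5% (simulation error about 0.5 points).

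So there is no confounding, only slight attenuation.

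**3. Omission when Phase 2 has a different mix.** Assume stratum HRs 1.8 and 1.5, with prevalences 20% and 25% in brand and 8% and 12% in generic. Treating the factors as independent, the average relative hazard is:
- Brand: (1 + 0.20 × 0.8)(1 + 0.25 × 0.5) = 1.16 × 1.125 = 1.305
- Generic: (1 + 0.08 × 0.8)(1 + 0.12 × 0.5) = 1.064 × 1.06 = 1.128
- Ratio 1.128/1.305 = 0.864, so a true HR of 3.54 reads as about 3.54 × 0.864 = 3.06.

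Approximate false non-inferiority:
- Brand events 40 × 0.13 × 0.95 = 4.94
- Generic events 160 × 0.95 × (1 − 0.87^3.06) = 52.7
- SE = √(1/4.94 + 1/52.7) = 0.471
- Φ(−1.645 + ln(3.54/3.06)/0.471) = Φ(−1.335) = 9.1%

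Simulating the Cox model with 40/160 gives 10.7% to 10.8% with centre only and 5.1% to 5.3% with both factors added.

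**4. Other scenarios (simulated).**

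| Assumption | True HR | Centre only | Both factors added |
|---|---|---|---|
| Stratum HRs 1.8/1.5, no imbalance | 1 | power 71.6–71.8% | 70.6–70.8% |
| Stratum HRs 1.8/1.5; brand 5%/10%, generic 12%/16% | 1 | power 67.6–68.3% | 69.5–71.3% |
| HR 2 each; elderly 25%→15%, ethnic 20%→10% from Phase 1 to 2 | 3.54 | HR 2.99; false non-inferiority 10.8% | HR 3.55; 5.4% |
| HR 2 each; elderly 15%→25%, ethnic 10%→20% | 1 | HR 1.17 | HR 1.01 |
| Phase 2 differs by another factor, HR 1.5 | 1 | HR 1.45 | HR 1.45 |
| Phase 2 differs by another factor, HR 0.67 | 3.54 | HR 2.45; false non-inferiority 23.9% | HR 2.49; 22.3% |

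Simulated power is below the formula's 81.2%, which is a large-sample approximation while the brand arm expects about five events. The comparison here is between columns.

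**5. Can the model carry two more terms?** At HR 1, events per parameter fall from 25/4 = 6.3 to 25/6 = 4.2. The simulated loss is about 1 point of power, and 0 to 2 points is a fair range.

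**The case against.** A reader might infer that dropping two randomisation strata biases the primary HR in itself. It does not: step 2 shows an HR of 1.00 with or without them when treatment is randomised. Nor do the documents show that the arms differ in age or ethnicity, or by how much either factor shifts risk. The 10.7% needs both factors imbalanced in the same direction. If the 20 randomised generic subjects resemble the brand arm, Phase 2 prevalences would have to be (0.08 × 160 − 0.20 × 20)/140 = 6.3% and (0.12 × 160 − 0.25 × 20)/140 = 10.1%, down from 20% and 25% under the same eligibility criteria and sites. That is a large shift. The figure illustrates a risk and does not forecast one.

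The second objection is that the remedy is partial. Where Phase 2 differs on something else, such as insurance or calendar time, the last two rows of the table show almost no benefit. This stands, and it limits what the fix may claim.

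Third, read literally, the intention-to-treat definition excludes Phase 2, and the confounding disappears. But sections 3.4, 4.2 and 6.2.8 count all 200 subjects, and 40 against 20 would give 60 × 0.13 × 0.95 = 7.4 events and about 49% power. The plan has to say which it means.

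Fourth, the plan gives a reason for keeping age/race models exploratory, and few events favour a small model. That argues for one term per factor. It does not justify leaving both out, given the cost in step 5. Section 6.2.7 also leaves the stratum categories undefined. If age cohort is the over-65 split of section 3.3, eligibility up to 70 makes the older group narrow, so collapsing may be needed.

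**Conclusion.** The point holds as a mismatch between randomisation and primary analysis whose importance comes from the non-randomised Phase 2. Within the 60 randomised subjects the omission causes no confounding. Across the 40 and 160 it leaves the primary HR open to any difference in age or ethnic mix. Under the assumed imbalances, the false non-inferiority rate is about double the nominal 5% with centre only and returns to about 5% with both factors added. If the mix is the same in both phases, little is at stake either way. The text mismatch and the 87.5% non-randomised share come from the documents; the stratum effects and prevalences are assumptions. The documents support neither the claim that the HR will be biased nor the claim that these two covariates would make the Phase 2 comparison equivalent to a randomised one. The change is worth making because it is cheap and the factors are ones the plan itself chose.

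**What to change.** - In section 4.2 and the Synopsis, add age cohort and ethnic group to the primary Cox model beside the centre indicators, as one binary term each. Define the categories in section 6.2.7 and give a rule for collapsing sparse ones.
- Keep the centre-only model as a named sensitivity analysis.
- State that the adjustment removes confounding by age and ethnicity only, and not by other differences between Phase 1 and Phase 2 subjects.
- Reconcile the Synopsis intention-to-treat definition with the inclusion of the 140 non-randomised subjects.

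Cost: recipient age, race and ethnicity are already collected (section 4.1), so no new data are needed. Expect about 0 to 2 points of power with balanced arms. Because the study is open-label and Phase 1 randomisation is described in the past tense, the change should be a dated amendment made before outcomes are compared by arm.
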